13.5 Procedures on Days 29, 57, 85, and 99/Early Termination

Prior to study drug administration (pre-dose procedures):

- directed physical examination;
- urine pregnancy test (except Day 99);
- interim medical/medication history;
- vital signs (temperature, respiratory rate, blood pressure and pulse);
- chem-20 (see Appendix B), CBC, and UA;
- adverse event assessment;
- measure disease activity (ESSDAI, PGA, Schirmer's, stimulated and unstimulated salivary flow);
- patient reported outcomes (ESSPRI, FACIT, Profile of fatigue, EQ-5D-L, Fatigue VAS, Neuropsychological analysis (Day 99 only);
- optional minor salivary gland biopsy (consented subjects) (Day 99 only);
- serum for study drug concentration and RNase activity;
- serum protein analysis;
- whole blood for gene expression profile
- whole blood for ESR;
- serum for anti-Ro-52/Ro-60 autoantibodies
- serum for total immunoglobulins, C3 and C4;
- serum for anti-RSLV-132 antibodies (Day 29 only);

After completion of above assessments:

- o study drug administration (except Day 99)

13.6 Procedures on Day 141

The following procedures will be performed on Day 141:

- directed physical examination;
- pregnancy test (serum);
- interim medical/medication history;
- vital signs (temperature, respiratory rate, blood pressure and pulse);
- adverse event assessment;
- serum for study drug concentration and RNase activity;
- serum for assessment of anti-RSLV-132 antibodies;

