3.5.3 Toxicology

The toxicology of RSLV-132 has been assessed in rats for periods up to 28 days and for up to 26 weeks in monkeys using either every-three-day dosing or weekly dosing schedules, respectively. In animal toxicology studies, RSLV-132 was well tolerated in rats and monkeys when given intravenously at doses up to 50 mg/kg/dose in monkeys, and up to 100 mg/kg/dose in rats for 4 weeks (5-10 doses) and for 26 weeks (26 doses) in the monkey (up to 50 mg/kg).

These dose levels were considered maximum feasible doses based upon dose volume and formulation concentration constraints. Clinical findings were limited to a minor increase in blood fibrinogen seen only in rats. Given the absence of effects upon any other coagulation parameters or any correlating anatomical pathology change, this transient observation was not considered adverse.

In the 4-week monkey study low titer (1:25) ADA responses were observed in several monkeys across all dose groups. In the 26-week monkey study five of the forty animals had high titer ADA responses which impacted exposure. However, in the rat study high titer ADA responses were observed across all dose groups, but the response had no impact on RSLV-132 exposure or pharmacological activity in either the monkey or rat studies. Comprehensive anatomical pathology evaluations in rats and monkeys did not elucidate any target organs aside from lymphoid hyperplasia in the spleen consistent with an immunogenic response to a foreign protein. Safety pharmacology parameters (CNS, respiratory, and cardiovascular systems) were examined in the context of the definitive monkey toxicology study. There were no test article-related clinical signs, or changes in, cardiovascular or respiratory parameters (electrocardiography, blood pressure, heart and respiration rates, and pulse oximetry). In

addition, the brain, lungs, and heart were evaluated microscopically in the rat and monkey studies. There were no microscopic changes in any of these tissues attributable to the test article with the exception of the presence of small numbers of hemosiderin-containing macrophages noted in the choroid plexus of the brains in 13 rats. These findings correlated with a strong ADA response. No further findings were noted in brain tissue.

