In the 26-week monkey study, one female given 30 mg/kg was sacrificed in moribund condition on Day 127 of the dosing phase; clinical observations included hunched posture and red periorbital skin while microscopic findings of perivascular/vascular inflammation and/or hemorrhage were present in multiple tissues. Although these changes were test article-related, they likely represented an immunogenic or hypersensitivity reaction to RSLV-132 and not a direct toxic effect. All remaining animals survived to their scheduled sacrifice and no other RSLV-132-related clinical observations were noted.

As RSLV-132 was well tolerated in animals following repeated injections occurring over a one to six-month period, the dosing regimen proposed for the clinical trial is not anticipated to be associated with any significant adverse events. Based upon the results of nonclinical studies, there are no findings which would preclude the continued investigation of RSLV-132 in clinical trials.

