6.3 Subject Withdrawal Criteria

Subjects will be informed that they are free to withdraw from the study at any time and for any reason. A subject should be discontinued from study drug treatment for any of the following reasons: AE which is either intolerable or poses safety concerns, pregnancy or disease worsening. The Investigator may also remove a subject from investigational treatment if, in the Investigator's opinion, it is not in the best interests of the subject to continue. Notification of discontinuation of investigational treatment will be made immediately to the Sponsor. In case of premature discontinuation of investigational treatment, efforts will be made to perform all protocol specified procedures for remaining study visit time points or at a minimum perform early termination assessments specified in Appendix A.

If a subject wishes to withdraw from the study, the site staff should confirm whether the subject is agreeable to continue the assessments without the investigational treatment or if they wish no further involvement in the study. In the latter case no further study-related evaluations will be performed and no additional data will be collected.

The date and the reason for discontinuation of investigational treatment or withdrawal from the study will be recorded on the subject's case report form. Subjects that withdraw after receiving study drug will not be replaced.

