12.1 Subject Population for Primary Endpoint Analysis

The effect of RSLV-132 on blood cell gene expression and serum protein levels will be compared between the two arms. Subjects who complete all treatment visits will be included in the primary analysis. Randomized patients who receive the incorrect therapy from that intended will be summarized in the group according to the therapy actually received. In the unlikely event of a patient commencing one study therapy and crossing over to the other, the data for that patient will be included in summaries and analyses with the original group.

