13.3 Baseline (Day 1) Procedures

Prior to study drug administration (pre-dose procedures):

- inclusion/exclusion criteria re-evaluated
- directed physical examination;
- pregnancy test (urine);
- interim medical/medication history;
- vital signs (temperature, respiratory rate, blood pressure and pulse);
- chem-21 (see Appendix B), CBC, and UA;
- AE Assessment;
- measure disease activity (ESSDAI, PGA);
- stimulated and unstimulated salivary flow;
- Schirmer's test;
- patient reported outcomes (ESSPRI, FACIT, Profile of fatigue, EQ-5D-L, Fatigue VAS, Neuropsychological analysis (at Newcastle University only));
- optional minor salivary gland biopsy (consented subjects);
- serum for study drug concentration and RNase activity;
- serum protein analysis;
- whole blood for gene expression profile;
- whole blood for ESR;
- whole blood for DNA analysis;
- serum for anti-Ro-52/Ro-60 autoantibodies;
- serum for total immunoglobulins, C3 and C4;
- serum for assessment of anti-RSLV-132 antibodies;

After completion of above assessments:

- study drug administration. Subjects will remain under observation in the clinic for at least 2 hours following the first administration of study drug. The clinic shall have resuscitation equipment available in close proximity to the infusion room.

13.4 Procedures on Days 8, 15, 43, and 71

Prior to study drug administration (pre-dose procedures):

- directed physical exam;
- pregnancy test (urine);
- interim medical/medication history;
- vital signs (temperature, respiratory rate, blood pressure and pulse);
- adverse event assessment;

After completion of above assessments:

- o study drug administration

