17 APPENDICES

17.1 Appendix A: Study Procedures

| Study Procedures | Screen (-60 to -1) | Baseline Day 1 | Day 8 | Day 15 | Day 29 | Day 43 | Day 57 | Day 71 | Day 85 | Day 99/ET | Day 141 | Day 176 Tel. FU | Day 211 Tel. FU EOS |
|---|--------------------|----------------|----------------|----------------|----------------|----------------|----------------|----------------|----------------|----------------|----------------|-----------------|---------------------|
| Acceptable visit window (days) ^f | | | ± 2 | ± 2 | ± 2 | ± 2 | ± 2 | ± 2 | ± 2 | ± 2 | ± 5 | ±10 | ±10 |
| Informed consent | X | | | | | | | | | | | | |
| Inclusion/exclusion | X | X | | | | | | | | | | | |
| Demographics/weight/height | X | | | | | | | | | | | | |
| Hepatitis, HIV tests | X | | | | | | | | | | | | |
| FSH (female subjects only) ^g | X | | | | | | | | | | | | |
| Whole blood for interferon signature | X | | | | | | | | | | | | |
| Physical exam | X | X ^a | X ^a | X ^a | X ^a | X ^a | X ^a | X ^a | X ^a | X ^a | X ^a | X ^a | |
| Pregnancy test | X ^b | X ^c | X ^c | X ^c | X ^c | X ^c | X ^c | X ^c | X ^c | X ^c | | X ^b | |
| Medical/medication history | X | X ^d | X ^d | X ^d | X ^d | X ^d | X ^d | X ^d | X ^d | X ^d | X ^d | X ^d | |
| Vital signs | X | X | X | X | X | X | X | X | X | X | X | X | |
| Chem-20, CBC, UA | X | X | | | X | | X | | X | X | | | |
| AE assessment | | X | X | X | X | X | X | X | X | X | X | X | X |
| ESSDAI, PGA, salivary flow, Schirmer's test | | X | | | X | | X | | X | X | | | |
| Patient reported outcomes | | X | | | X | | X | | X | X | | | |
| Minor salivary gland biopsy (consented subjects) | | X ¹ | | | | | | | | X | | | |
| Serum for study drug concentration and RNase activity | | X | | | X | | X | | X | X | X | | |
| Serum for protein analysis | | X | | | X | | X | | X | X | | | |
| Whole blood for gene expression | | X | | | X | | X | | X | X | | | |
| Whole blood for ESR (performed by local laboratory) | | X | | | X | | X | | X | X | | | |
| Whole blood for DNA analysis | | X | | | | | | | | | | | |
| | | | | | | | | | | | | | |
| Serum for anti-Ro-52 and anti-Ro-60 autoantibodies | X | X | | | X | | X | | X | X | | | |
| Serum for total immunoglobulins, C3 and C4 | | X | | | X | | X | | X | X | | | |
| Serum for anti-RSLV-132 antibodies | | X | | | X | | | | | | X | | |
| Study Drug administration | | X ^e | X ^e | X ^e | X ^e | X ^e | X ^e | X ^e | X ^e | | | | |

Abbreviations: ET = Early Termination, EOS = End of Study

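### Anti-drug antibodies are not sampled at Day 99/Early Termination, so a subject whose last visit is Early Termination has no antibody result after Day 29

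*Protocol*

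**What the plan says.** **The risk.** Protocol section 3.5.3 states: "In the 26-week monkey study five of the forty animals had high titer ADA responses which impacted exposure". It also reports that "one female given 30 mg/kg was sacrificed in moribund condition on Day 127 of the dosing phase", and comments: "Although these changes were test article-related, they likely represented an immunogenic or hypersensitivity reaction". Section 3.7 notes that protein drugs of this kind may cause life-threatening anaphylaxis, and that none had been seen with RSLV-132. Sections 3.6.1 and 3.6.2 report no ADA-positive subject in the single-dose study and no confirmed positive in the 113-day multiple-dose study in SLE.

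**The sampling.** ADA is drawn before the first dose at Baseline (13.3), on Day 29 and on Day 141 (13.6). Section 13.5, which covers Days 29, 57, 85 and 99/ET, limits it to "serum for anti-RSLV-132 antibodies (Day 29 only"). The Appendix A row "Serum for anti-RSLV-132 antibodies" is marked at the same three visits and is blank at Day 99/ET. The Day 99/ET visit does draw serum for drug concentration and RNase activity.

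**Stopping early.** Section 6.3 asks for efforts to complete all remaining visits after premature discontinuation, "or at a minimum perform early termination assessments specified in Appendix A".

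**The concern.** The document identifies an immune response to the drug as a risk that can affect both safety and exposure. The visit it falls back on when a subject stops treatment collects evidence of exposure but not of the immune response. A subject taken off drug for a suspected immune reaction, seen once at ET and not again, leaves nothing with which to confirm or exclude ADA. If that subject's drug level or RNase activity is low, the loss of exposure is visible but its cause is not. Safety and tolerability is a secondary endpoint, and no analysis plan can recover a sample that was never drawn.

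**Working it through.** The protocol states no figure on this point to reproduce (section 12.3 gives no power calculation). The check sets the schedule against the dosing days.

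**Inputs.** Infusions on Days 1, 8, 15, 29, 43, 57, 71 and 85 (1.7, 5.3). ADA on Days 1, 29 and 141, with Day 29 pre-dose (13.3, 13.5, 13.6, Appendix A). Half-life about 16 days (3.6.1). 28 subjects randomized 3:1 (1.7).

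**1. Doses and gaps.**
- Infusions before the Day 29 sample: Days 1, 8 and 15 = 3 of 8. Infusions from Day 29 on: 5 of 8.
- Gaps now: 29 − 1 = 28 days and 141 − 29 = 112 days.
- Gaps with a Day 99 sample: 28, 99 − 29 = 70 and 141 − 99 = 42 days. The longest falls from 112 to 70.

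**2. What each type of subject yields.**

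| Subject | ADA results now | With ADA at Day 99/ET |
|---|---|---|
| Completes to Day 141 | Baseline, Day 29, Day 141 | adds Day 99 |
| Stops after Day 29, attends ET only | Baseline, Day 29 | adds ET |
| Stops before Day 29, attends ET only | Baseline only (pre-dose) | adds ET, the only post-dose result |
| Stops, declines all further contact | no further sample | no further sample |

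The second and third rows are the gap. The protocol gives no dropout rate, so their number is unknown. The active arm is 28 × 3/4 = 21, so each such active subject is 1/21 = 4.8% of the arm.

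**3. Would a Day 99 sample be readable?** Circulating drug can interfere with ADA detection. Assume simple first-order decline and add the residual of each dose, 0.5^(days since dose/16), in units of one dose:
- Day 29 pre-dose: 0.5^(28/16) + 0.5^(21/16) + 0.5^(14/16) = 0.297 + 0.403 + 0.545 = 1.25.
- Day 99, same sum over eight doses (98, 91, 84, 70, 56, 42, 28 and 14 days earlier): 0.014 + 0.019 + 0.026 + 0.048 + 0.088 + 0.162 + 0.297 + 0.545 = 1.20.
- Day 141: 1.20 × 0.5^(42/16) = 1.20 × 0.162 = 0.19.

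Day 99 carries about the same drug load as the Day 29 sample that the protocol already accepts. Day 141 carries about one sixth of it.

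**4. Do earlier human data make the sample unnecessary?** With no positives in n treated subjects, the one-sided 95% upper limit is 1 − 0.05^(1/n).
- 24 multiple-dose SLE subjects: 1 − 0.05^(1/24) = 11.7%.
- 48 treated subjects, both studies pooled: 1 − 0.05^(1/48) = 6.1%, though 24 of these had one dose only.

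These are limits, not estimates. They show only that the earlier studies cannot exclude ADA in a few percent of subjects. The monkey figure, 5/40 = 12.5%, is an animal rate for a human protein and is not carried over to this trial.

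**The case against.** **Section 6.3 seeks all remaining visits first.** That includes Day 141 and its ADA sample; ET is only the fallback. Section 10.6 also requires follow-up of causally related events until they resolve, stabilize or are explained. This stands and narrows the gap to subjects who attend ET and do not return. It does not close it, because section 10.6 names no ADA sample.

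**Day 141 is the better single time point.** It has the least circulating drug, and every subject who reaches it is sampled. This also stands. It is a reason to keep Day 141, not to leave ET empty.

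**No ADA has been confirmed in people so far.** True, and it keeps the weight of the point low.

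Four stronger readings are tempting, and the documents do not support them:
- A reader might infer that sections of the protocol contradict each other on ADA sampling. Section 13.5 and Appendix A agree.
- A reader might infer that subjects stopped for an immune reaction generally go unsampled. Section 6.3 asks for their remaining visits.
- A reader might infer that the 30 mg/kg animal overturns the 5-fold margin in 1.7 and 3.4. Section 3.5.3 says the changes were not a direct toxic effect, and nothing shown allows a different reading.
- A reader might infer that infusions 2 to 8 are unobserved, since section 13.3 says "Subjects will remain under observation in the clinic for at least 2 hours following the first administration of study drug". Administration details are left to the Study Drug Reference Guide, which is not shown, and the sentence on resuscitation equipment is not limited to the first dose. The animal event, with inflammation and hemorrhage in several tissues on Day 127, was also not described as an acute infusion reaction.

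**Conclusion.** The point holds as a design weakness that is cheap to mend. ADA is missing from the visit that serves as the minimum for subjects who stop treatment. A subject last seen there has no ADA result after Day 29, after three of eight infusions at most, and none post-dose if stopped before Day 29. For the trial as a whole, 112 days and five infusions lie between the last two ADA samples. Subjects who reach Day 141 are unaffected apart from that gap.

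The schedule finding needs no assumption. The comparison of drug loads rests on first-order decline with a 16-day half-life. How many subjects would fall in the gap, and how far circulating drug lowers assay sensitivity, cannot be derived from the protocol.

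Two minor notes. Section 3.5.3 says ADA impacted exposure in five monkeys and then says the response had no impact in either species; the second statement should name the studies it covers. The protocol could also say whether post-infusion observation applies after infusions 2 to 8, or point to the guide that does.

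**What to change.** - In section 13.5, change '(Day 29 only)' to '(Day 29 and Day 99/ET)' for the ADA sample.
- Mark the Day 99/ET cell in the ADA row of Appendix A.
- Add an unscheduled ADA sample at any suspected hypersensitivity reaction.
- Keep Day 141 as the low-drug sample.

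Cost: one extra serum aliquot per subject, at most 28 scheduled assays, at a visit that already draws serum, plus occasional unscheduled samples. Dose, dosing days and sample size do not change. The price in interpretation is some loss of ADA sensitivity from circulating drug, so a negative result at Day 99/ET is weaker evidence than a negative at Day 141 and should be read together with the drug level from the same visit. The change does not help with a subject who declines all further contact.

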13.7 Telephone Follow-up on Days 176 and 211 (End of Study)

Subjects will be contacted via telephone at Day 176 and Day 211 to collect follow up information on any adverse events that were ongoing at Day 141, and to determine if there are any new reportable adverse events (e.g. positive relationship to the investigational product). If new reportable adverse events are identified it will be requested that the subject return to the clinic for an unscheduled visit and assessment by the Principal Investigator.

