1.11 Evaluations by Day

- Screening Procedures:
 - informed consent;
 - assess inclusion/exclusion criteria;
 - demographic data;
 - weight and height;
 - physical examination;
 - complete medical and medication history;
 - vital signs;
 - hepatitis B, C, and HIV antibody tests;
 - serum pregnancy test;
 - chem-21 (see Appendix B), CBC, and UA;
 - interferon-stimulated gene expression analysis (whole blood);
 - anti Ro-52/Ro-60 autoantibodies;
 - FSH (when required to confirm menopause in female subjects)

- Baseline Procedures:
 - confirmation of inclusion/exclusion criteria;
 - physical examination;
 - adverse event baseline assessment;
 - interim medical and medication history;
 - vital signs;
 - measurement of disease activity (ESSDAI, PGA, Schirmer's, stimulated and unstimulated salivary flow);
 - measurement of patient reported outcomes (ESSPRI, FACIT, Profile of fatigue, EQ-5D-L, Fatigue VAS, Neuropsychological analysis);
 - optional minor salivary gland biopsy;
 - urine pregnancy test;
 - chem-21 (see Appendix B), CBC, and UA;
 - serum for study drug concentration and RNase activity;
 - serum for serum protein analysis;
 - whole blood for ESR
 - whole blood for DNA analysis;
 - whole blood for measurement of RNA gene expression;
 - serum for anti Ro-52/Ro-60, total immunoglobulins, C3, and C4;
 - serum for anti-RSLV-132 antibodies;
 - study drug administration.

Additional Procedures:

The following procedures will be performed at various visits during the study. A total of 9 post-baseline visits will occur; once weekly for two weeks, then every two weeks for 14 weeks, plus one further visit 8 weeks after the last study drug administration. There will then be two additional telephone contacts made to subjects at weeks 13 and 18 after the last dose, to monitor any potential late-emerging adverse events. See section 13 and the schedule of events for the specific procedures and collection time points.

- physical exam;
- vital signs;
- adverse event assessment;
- medication history;
- measurement of disease activity (ESSDAI, PGA, Schirmer's test, stimulated and unstimulated salivary flow);
- optional minor salivary gland biopsy;
- measurement of patient reported outcomes (ESSPRI, FACIT, Profile of fatigue, EQ-5D-L, Fatigue VAS, Neuropsychological analysis);
- serum sample for study drug concentration and RNase activity;
- serum for protein analysis;
- whole blood for ESR
- whole blood for DNA analysis;
- whole blood for gene expression profile;

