10 ASSESSMENT OF SAFETY

Safety of the treatment will be compared between the two groups by assessing adverse events and laboratory results as well as any physical findings that have changed from baseline.

All patients who have received an infusion with either RSLV-132 or placebo will be included in the overall analysis of safety. All data relating to safety will be listed and summarized by treatment group using descriptive statistics. The change from baseline for each of the vital signs parameters will also be computed and included in individual patient listings and descriptive summaries.

Deaths that occur during the study and the proportion of subjects discontinuing the study due to adverse events will be summarized by treatment group.

All adverse events will be coded and tabulated by MedDRA System Organ Class (SOC) and preferred term (PT) and presented in descending frequency. Adverse events will also be tabulated by severity and relationship to the study medication. Serious adverse events will be summarized separately.

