10.3 Adverse Event Reporting

All AEs, both serious and non-serious, will be recorded on the AE CRF at each visit from the time the subject receives the first dose of study medication until Day 211, the final telephone contact with the subject. Any untoward event occurring between screening and baseline and deemed directly related to a study procedure by the investigator will be recorded on the AE CRF.

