10.4 Serious Adverse Event Reporting Requirements

SAEs will be reported to Resolve at [contact] on the SAE report form within 24 hours of awareness of the event by the investigator.

In the event that the investigator does not become aware of the occurrence of an SAE immediately, the investigator is to report the event within 24 hours of his/her first awareness of the SAE.

Any SAE occurring any time after the reporting period must be promptly reported if a causal relationship to investigational product is suspected.

The initial report should include as much relevant information as possible but at a minimum should include subject number, date of event onset, event term/description of event, investigator's assessment of relationship to study drug.

For all SAEs, the investigator is obligated to pursue and provide information to Resolve or its designee in accordance with the timeframes for reporting specified above. In addition, an investigator may be requested by Resolve to obtain specific additional follow-up information in an expedited fashion. This information may be more detailed than that captured on the AE case report form. In general, this will include a description of the AE in sufficient detail to allow for a complete medical assessment of the case and independent determination of possible causality. Information on other possible causes of the event, such as concomitant medications and illnesses must be provided. All new information including final outcome should be submitted as soon as possible.

Suspected Unexpected Serious Adverse Reactions (SUSARs) are subjected to expedited reporting and should be unblinded prior to submission to the regulatory authority. Fatal or life-threatening SUSARs must be reported to regulatory agencies and IEC by the sponsor as soon as possible, but no later than 7 days after first awareness of the reaction. Any additional relevant information must be sent within 8 days of the first report. Non-fatal or non-life-threatening SUSARs must be reported as soon as possible but no later than 15 days after first awareness of the reaction.

All UK-relevant SUSARs should be reported to the MHRA. "UK-relevant" includes SUSARs originating in the UK and SUSARs originating outside the UK where the sponsor has an ongoing trial in the UK involving the same medicinal product. For the IEC, only SUSARs occurring within the UK should be reported.

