10.8 Causality Assessment

The investigator's assessment of causality must be provided for all AEs (serious and non-serious). Causality is determined as not related, possibly related, or definitely related according to the following definitions:

- Not related: The event can be readily attributed to other factors such as the subject's clinical state, environmental factors, or other concomitant medications or therapies administered.
- Possibly Related: Follows a reasonable temporal sequence from administration and is unlikely to be attributed to the subject's clinical state or environmental factors or other therapies administered.
- Definitely related: Clear-cut temporal association with study drug administration with improvement on cessation of study drug AND cannot be readily attributed to other factors such as the subject's clinical state, environmental factors, or other concomitant medications or therapies administered.

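### The Day 176 and 211 calls ask only for new *reportable* adverse events, although Section 10.3 requires every adverse event to be recorded up to Day 211

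*Protocol*

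**What the plan says.** Section 10.3 sets the recording rule: "All AEs, both serious and non-serious, will be recorded on the AE CRF at each visit". The period runs "from the time the subject receives the first dose of study medication until Day 211, the final telephone contact with the subject". The rule has no causality condition and names the last call as its end point.

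Other sections agree:

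- Section 10.5 sends non-serious AEs to the AE case report form, again without a causality condition.
- Appendix A has a row "AE assessment", marked at Days 176 and 211 as at every contact from Baseline on, with no limiting footnote.
- Section 1.11 gives the purpose of the calls as "to monitor any potential late-emerging adverse events".
- Section 10.8 says that the investigator's "assessment of causality must be provided for all AEs (serious and non-serious") as a matter of course.

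Section 13.7 is the instruction for the calls themselves. It asks for follow-up of all AEs still ongoing at Day 141, but for new events it asks only whether there are "any new reportable adverse events (e.g. positive relationship to the investigational product"). If there are, the subject is asked to return for an unscheduled assessment by the Principal Investigator.

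**The concern.** Section 13.7 treats the two kinds of event differently. Ongoing AEs are taken without restriction, while new ones must first be *reportable*. The protocol does not define that word as a class of AE, and the only example given is a positive relationship to the product. Site staff making the call could reasonably read it as a relatedness filter.

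The safety tables would then rest on two capture rules. Section 10 summarizes AEs by treatment group and adds: "Adverse events will also be tabulated by severity and relationship to the study medication". Capture would be complete up to Day 141 and selected by relatedness afterwards. Late non-serious AEs would be undercounted, and the related share of late AEs would be too high. An event that was never written down cannot be restored by any later analysis rule.

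**Working it through.** The protocol states no figure to reproduce here. The check compares the texts and then counts days.

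**1. The rules side by side**

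| Source | New AEs covered, Day 141 to Day 211 | Causality condition |
|---|---|---|
| Section 10.3 | all, serious and non-serious | none |
| Section 10.5 | non-serious AEs go on the form | none |
| Appendix A | AE assessment marked at both calls; scope not stated | none |
| Section 1.11 | late-emerging AEs | none |
| Section 13.7 | *reportable* AEs only | relationship, as the sole example |

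**2. Does causality decide recording anywhere else?** Section 10.8 asks for a causality judgement on every AE, so unrelated AEs must be on record. Section 10.4 does use suspected causality as a condition, but only after the reporting period has closed: "Any SAE occurring any time after the reporting period must be promptly reported if a causal relationship to investigational product is suspected". That period ends at Day 211 under Section 10.3, so this condition does not reach the two calls.

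**3. Order of judgement.** Under Section 13.7 an event is classed as reportable on the telephone, and the Principal Investigator assesses it only if it passes. Section 10.8 requires the investigator's own causality assessment for all AEs. The protocol does not say who makes the first judgement.

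**4. Length of the exposed period** (visit days from Appendix A; last dose Day 85)

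- Share of the recording period: (211 − 141) / (211 − 1) = 70 / 210 = 33.3%.
- Share of follow-up after the last dose: 70 / (211 − 85) = 70 / 126 = 55.6%.
- Shortest with the visit windows (Day 141 + 5, Day 211 − 10): 201 − 146 = 55 days; 55 / (201 − 1) = 27.5%.
- Longest (Day 141 − 5, Day 211 + 10): 221 − 136 = 85 days; 85 / (221 − 1) = 38.6%.
- Scheduled AE assessments: 2 of the 12 marked in Appendix A, or 2 of 11 without the pre-dose Baseline assessment.

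**5. Weight of one event.** With 28 subjects randomized 3:1, the planned arms are 21 and 7. One subject whose only occurrence of an event is missed changes an incidence by 1/21 = 4.8 percentage points in the active arm or 1/7 = 14.3 in the placebo arm.

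**6. AEs lost.** This cannot be computed, because the protocol gives no AE rate for this late period.

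**The case against.** The strongest reply is that the sections can be read together. The protocol uses *report* broadly: Section 10.3 is headed as AE reporting and covers everything, and Section 10.5 has non-serious AEs reported on the form. On that usage a reportable AE is any AE, and the parenthesis is one illustration, introduced by *e.g.* Section 13.7 never says that unrelated AEs are to be left out, and a site that follows Section 10.3 loses nothing.

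This makes the filter likely rather than certain, and the conclusion is worded accordingly. It does not remove the conflict. If *reportable* meant every AE, the relationship example would serve no purpose, and every trivial new event would prompt a request to return to the clinic. The contrast with the unrestricted wording for ongoing AEs would also go unexplained.

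Other points stand as limits:

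- Appendix A schedules an assessment but states no scope; the all-AE rule rests on Sections 10.3 and 10.5.
- The percentages measure calendar time, not data lost.
- Exposure is low in this period. Assuming the half-life of about 16 days from the single-dose study (Section 3.6.1) applies here, Day 141 lies 56 / 16 = 3.5 half-lives after the last dose (about 9% remaining) and Day 211 lies 126 / 16 = 7.9 (under 0.5%). This cuts both ways: drug effects are less likely, but new events are also more readily judged unrelated and so dropped, although the follow-up exists to detect delayed events.
- The safety analysis is descriptive, and no separate table of late AEs is specified, so the effect would be diluted in whole-study tables.

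**Conclusion.** The concern holds. Section 13.7 gives a narrower instruction for new AEs than Section 10.3 requires for the same contacts. New-onset, non-serious AEs judged unrelated could go unrecorded between Day 141 and Day 211. That is 70 days, or 33% of the recording period (28% to 39% across the visit windows), and 56% of post-dose follow-up.

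This assumes that at least some sites take Section 13.7 at face value; the wording makes that likely but not certain. Serious AEs within the period, related AEs and AEs ongoing at Day 141 are captured on either reading. Both arms follow the same blinded procedure, so the fault is incomplete and inconsistent capture, not a bias in a known direction between arms. No efficacy result is touched. It should be corrected, because the loss is irreversible and the correction is simple.

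**What to change.** Reconcile Section 13.7 with Section 10.3 and Appendix A so that one recording rule applies up to Day 211. Possible wording for the calls:

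> The contact will obtain follow-up on every adverse event still open at Day 141 and establish whether any new adverse event has occurred, whatever its suspected relationship to the product. All are entered on the AE CRF under Section 10.3.

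Keep the criterion for the unscheduled visit in a sentence of its own, so that it does not govern recording, and either define *reportable* there or replace the word. This review takes no position on which events should prompt a visit.

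The cost is one sentence in Section 13.7 and a matching line in any script used for the calls, which already take place. Sites would enter a few more non-serious AEs, some known only from the subject's account by telephone.
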